## 1.4 Clinical Data to Date

A recently published meta-analysis of XR-NTX found an association with reduction in heavy drinking days (weighted mean difference -4.6%; 95% CI, -8.5% to -0.56%). **XR-NTX is safe and effective among both individuals who are abstinent and actively drinking.**

The efficacy of XR-NTX in the treatment of alcohol dependence was evaluated in a 24 week, placebo-controlled, multi-center, double-blind, randomized trial of alcohol-dependent (DSM-IV criteria) outpatients. Subjects were treated with an injection every 4 weeks of XR-NTX 190 mg, XR-NTX 380 mg or placebo. Oral naltrexone was not administered prior to the initial or subsequent injections of study medication. Psychosocial support was provided to all subjects in addition to medication. Subjects treated with XR-NTX 380 mg demonstrated a greater reduction in days of heavy drinking than those treated with placebo. Heavy drinking was defined as self-report of 5 or more standard drinks consumed on a given day for male patients and 4 or more drinks for female patients. Among the subset of patients (n=53, 8% of the total study population) who abstained completely from drinking during the week prior to the first dose of medication, compared with placebo-treated patients, those treated with XR-NTX 380 mg had greater reductions in the number of drinking days and the number of heavy drinking days. In this subset, patients treated with XR-NTX were also more likely than placebo-treated patients to maintain complete abstinence throughout treatment. The same treatment effects were not evident among the subset of patients (n=571, 92% of the total study population) who were actively drinking at the time of treatment initiation.

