The infrastructure to support timely data-sharing and coordination of services between health and social service institutions is underdeveloped, resulting in failed navigation, frustrating providers and patients. By helping to address these difficulties, care management (CM) interventions targeting frequent ED users, including our pilot, have demonstrated reductions in the use of costly health services but have not reported an effect on drinking. Low-barrier, non-abstinence based, housing programs that include intensive care management (e.g. Housing First) have been associated with reduced use of costly public resources as well as alcohol use and alcohol-related harm. These community-based programs, however do not yet partner directly with EDs to coordinate care or to identify program subjects.

Well-controlled clinical trials— such as the “Combining Medications and Behavioral Interventions for Alcoholism” (COMBINE) study— have demonstrated the efficacy of behavioral and pharmacologic treatments for alcohol dependence. Specifically, naltrexone, an FDA-approved opioid receptor antagonist, has been shown to reduce craving, heavy drinking, and healthcare utilization and associated costs. The pharmacokinetic properties of the extended-release preparation (XR-NTX), providing steady-state medication concentrations with injections every 4 weeks, are promising and particularly well suited for this often medically disengaged population at risk of non-adherence. It is safe and effective among both individuals who are abstinent and actively drinking. Its feasibility in primary care and other non-specialized medical settings has been demonstrated at our institution, where effectiveness studies are ongoing. A recent pilot of XR-NTX plus harm reduction counseling in a community-based low-barrier housing program (in which abstinence is not required and intensive care management is provided) suggests a potentially more robust effect and high acceptability among a population similar to the one we are studying. However, neither XR-NTX nor other pharmacotherapy for alcohol dependence has been studied in the ED. A critical need exists to refine and test the use of medications to treat alcohol dependent individuals in clinical settings where they frequently present, such as the ED.

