in the study may be intoxicated from alcohol when they arrive in the emergency department, but will not be enrolled until medically stable and clinically sober. Patients (potential subjects) may be placed into ED observation for the extended duration of care necessary to achieve this state. If this represents a minor deviation from the VIVITROL labeling, it may affect efficacy but should not represent an additional safety concern. XR-NTX is not aversive therapy and does not cause a disulfiram-like reaction as a result of ethanol ingestion. XR-NTX has been shown to be safe and effective among both individuals who are abstinent and actively drinking. A subject's ability to abstain from drinking prior to an initial XR-NTX injection may predict treatment response. However, this association has not been seen in all studies, including an XR-NTX pilot conducted in Bellevue Hospital primary care. Further, the administration of XR-NTX for the treatment of alcohol dependence users in this study is consistent with current clinical care for alcohol dependent patients in other clinical settings, including Bellevue Hospital Ambulatory care. The administration of XR-NTX in our protocol is based on protocols of ongoing studies of XR-NTX for alcohol dependence in other clinical and community settings, including [name] XR-NTX study in Bellevue Hospital ambulatory care (R01AA020836; S12-02263) and [name]' study in a Seattle community housing program (R01 AA022309), which the FDA also determined was exempt from IND reporting. Also of note, the investigation is not intended to be reported to FDA as a well-controlled study in support of a new indication and there is no intent to use it to support any other significant change in the labeling or advertising of the drug. The investigation does not involve a route of administration, dose, patient population, or other factor that significantly increases the risk associated with the use of the drug product.

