## 7 Statistical Plan

### 7.1 Sample Size Determination

Naltrexone has not demonstrated a robust treatment effect; however, most studies did not use the XR-preparation, are limited by poor adherence, and did not include this higher-severity population or other intervention components. We do not know what the “ideal” population for XR-NTX is, but posit that it may have a greater effect size in this more severely affected population than amongst the higher socioeconomic status population historically targeted. A recent pilot of XR-NTX suggests a possible greater effect (and acceptability) in a population similar to ours. Our literature search yielded no studies of initiating pharmacotherapy for alcohol dependence in the ED. There are only limited data on XR-NTX effects on several long-term outcomes of interest, including healthcare use, treatment engagement, and quality of life measures. ED-based case management studies demonstrate promising healthcare utilization outcomes, but most were uncontrolled and overestimated effect because of regression to the mean. The heterogeneity in study designs, interventions, and cohort characteristics precludes meta-analysis.

Determining sample size is challenged by limitations in the existing data and heterogeneity of populations. Definitively testing the relative effects of intervention components may require additional arms with as many as 75 to 200 subjects in each. Thus, we chose to start with the strongest intervention and compare it to standard care to maximize the likelihood of seeing an effect and of exploring effect size on various outcomes. The 2-arm design will minimize the loss of power and allow us to focus on the primary goal of assessing feasibility.

The first phase of study will be a feasibility and acceptability study, through which we will obtain preliminary data to inform the power analysis for the subsequent definitive trial. In the first phase, we plan to pilot the study in 50 subjects. In the second phase of study, we project enrolling 125 subjects in each of the two arms to definitively test the intervention’s effect on multiple outcomes of interest. Thus, we

CONFIDENTIAL

This material is the property of the NYU School of Medicine and Langone Medical Center. Do not disclose or use except as authorized in writing by the study sponsor

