### **Aim 3: Patient-Level Predictors of Effectiveness:**

Baseline and longitudinal predictors of interest in naltrexone alcohol treatment efficacy and effectiveness trials include gender, ethnicity, mu opioid receptor genotype, and ancillary alcohol behavioral treatment involvement. Naltrexone's relative ineffectiveness in African American clinical trial sub-populations, including in the COMBINE trial, is possibly mediated by low rates of the Asp40 OPRM1 functional allele in persons of African descent, who are primarily Asn40 homozygous. This Asp40 (A118G, 'G' allele) OPRM1 functional single nucleotide polymorphism has been shown to be associated with successful treatment with naltrexone. A pilot conducted by [name] at Bellevue did find a strong association between persons involved at baseline or who became involved during primary care XR-NTX treatment with specialty alcohol treatment and/or Alcoholics Anonymous. Thus, we hypothesize a priori that there will be less robust effectiveness among African Americans; voluntary specialty alcohol treatment and Alcoholics Anonymous involvement, and presence of the Asp40 OPRM1 SNP will be associated with treatment effectiveness. We note, however, that these analyses will be exploratory, as the study is not powered to carefully test these secondary hypotheses.

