We will collect patient-level characteristics data to explore the association of patient-level characteristics (e.g. sex, race) with effectiveness. We will be able to carefully track prior detox admissions and concurrent 12-step and specialty alcohol treatment involvement in the proposed trial in order to estimate associations with treatment effectiveness. Multivariate models will be used to identify patient characteristics associated with treatment success. The analysis will utilize a logistic regression with an indicator variable for treatment and covariate terms for baseline potential prognostic indicators, including African American ethnicity, baseline drinking severity, and status of housing, social support, quality of life, and OPRM1 genotype. Odds ratios will be calculated to quantify the risk to treatment failure of significant predictors. As originally proposed, naltrexone appears most effective at reducing heavy drinking, as opposed to producing complete abstinence. A harm reductionist perspective delineating treatment success from failure is particularly important in this population having a greater severity of AUD and psychosocial dysfunction. All traditional alcohol treatment trial clinical endpoints, including continuous

CONFIDENTIAL

This material is the property of the NYU School of Medicine and Langone Medical Center. Do not disclose or use except as authorized in writing by the study sponsor

drinking and heavy drinking variables, as well as the %CDT biomarker, the change in CDT, and the combined CDT-GGT equation, which are specific for heavy drinking, are of great interest, and will be reported.

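### Aim 3 does not name pre-injection abstinence and its model has no treatment interaction, so as written it estimates prognosis and cannot show whether abstinence modifies the treatment effect

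*Combined protocol and SAP*

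**What the plan says.** Section 1.4 states in bold that "XR-NTX is safe and effective among both individuals who are abstinent and actively drinking", and section 1.1 makes the same statement: "It is safe and effective among both individuals who are abstinent and actively drinking". The next paragraph of 1.4 draws on the prescribing information. It reports that 380 mg beat placebo on heavy drinking days in the whole trial. It also reports that the 53 patients who had not drunk in the week before the first dose did better on drinking days, heavy drinking days and complete abstinence. It adds: "The same treatment effects were not evident among the subset of patients (n=571, 92% of the total study population) who were actively drinking" when treatment began.

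Section 1.6.1 repeats the favourable statement ("XR-NTX has been shown to be safe and effective among both individuals who are abstinent and actively drinking") but with context. It concedes that dosing without prior outpatient abstinence could affect efficacy. It says that "A subject's ability to abstain from drinking prior to an initial XR-NTX injection may predict treatment response", and then notes that not all studies found this, including a pilot in primary care at the same hospital.

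In section 7.2.2, the Aim 3 predictors of interest "include gender, ethnicity, mu opioid receptor genotype, and ancillary alcohol behavioral treatment involvement". The model is a logistic regression with an indicator for treatment and covariate terms for baseline prognostic indicators, "including African American ethnicity, baseline drinking severity, and status of housing, social support, quality of life, and OPRM1 genotype". No product term is stated. The analyses are declared exploratory and not powered.

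**The concern.** Aim 3 asks which patient characteristics go with effectiveness, so that treatment choice can be informed (section 2). That is a question about effect modification. The protocol's background names one candidate modifier tied directly to the drug, abstinence just before the first injection, and Aim 3 leaves it out.

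The candidate matters in this population. Entry requires at least two heavy drinking days a week (section 4.1), and subjects may be intoxicated on arrival (section 1.6.1), so most are likely to resemble the actively drinking majority of the label trial.

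The form of the model is the larger gap. Even the characteristics that are listed enter only as covariates. If the trial shows little effect on drinking, or a clear one, the Aim 3 model will not show whether the effect differed with recent abstinence.

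**Working it through.** **1. The label split.** Inputs from section 1.4: 53 abstinent, 571 drinking. 53 + 571 = 624; 53/624 = 8.5% and 571/624 = 91.5%. These agree with the printed 8% and 92%.

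**2. What the Aim 3 model can estimate.** Let T be treatment, X the listed covariates and A days abstinent before randomisation.

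- As written: logit P(success) = a + b·T + c·X. The treatment odds ratio is exp(b) at every value of X. The coefficients c say who does better over both arms together, which is prognosis.
- With the added terms: logit P(success) = a + b·T + c·X + e·A + f·T·A. The treatment odds ratio is exp(b + f·A), and f measures modification by abstinence. For a continuous drinking outcome the same terms enter a linear model.

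Adding A as a covariate alone (the term e·A) would not close the gap. The term f·T·A is needed.

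**3. Is the variable obtainable in both arms?** Yes. A 30-day TLFB is taken at enrolment (sections 6.1 and 7.2.1), and Aim 2c already uses a 7-day window. Randomisation follows all baseline assessments (section 4.3.5), and the first injection is given at the same visit (section 6.1). Days abstinent before randomisation is therefore a true baseline variable and stands in for pre-injection abstinence, including in the arm that gets no injection.

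**4. Is it already covered by baseline drinking severity?** Not necessarily. The plan does not define severity. Two subjects with the same 30-day count of heavy drinking days can differ in how many of the last 7 days were dry, and the label subgroup was defined by the last week.

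**5. Precision.** The documents define no success event or rate for the logistic model, so a continuous outcome with common SD and 1:1 allocation is used as an approximation. For a yes/no split with proportion p abstinent:

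SE = SD × √[4/(N·p) + 4/(N·(1−p))]; minimum detectable interaction = (1.96 + 0.84) × SE (80% power, two-sided 0.05).

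- N=300, p=0.085: √(4/25.5 + 4/274.5) = 0.414; × 2.80 = **1.16 SD**
- N=250, p=0.085: 1.27 SD
- N=50, p=0.085: 2.84 SD (about 4 abstinent subjects)

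The prevalence in this trial is not stated; 8.5% is borrowed from the label trial. Over an assumed 5% to 50%, the N=300 figure runs from 1.48 to 0.65 SD, and power for a 0.4 SD interaction runs from 11% to 41%.

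For a count of days, SE per 1 SD of the count = 2·SD/√N. At N=300, 2/√300 = 0.115; × 2.80 = 0.32 SD. At N=250, 2/√250 = 0.126; × 2.80 = 0.35 SD. If most subjects have no abstinent days, the SD of the count is small and the effect per day is poorly estimated.

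No dropout is applied anywhere.

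**The case against.** Several points on the other side stand. Section 1.6.1 is candid: it names the possible predictor, the possible loss of efficacy and the contrary evidence. Aim 3 is declared exploratory and unpowered. Its covariate list is open, it includes baseline drinking severity, and section 2 also names baseline drinking, so the sponsor could derive abstinence without amending anything. The interaction may also be very imprecise. If the entry criterion is read over the same 7 days, a subject can have at most 7 − 2 = 5 days without heavy drinking, and complete abstinence for the week is excluded.

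These points lower the weight of the concern but do not remove it. An open list leaves the choice until after the data are seen. An open covariate list still contains no interaction. Mixed evidence is a reason to estimate the term.

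A reader might go further and infer that the drug has no effect in active drinkers, so that the trial is badly underpowered. The documents do not support this. The label summary says that the same effects were not evident in drinkers, which is not a finding of zero, and the trial was positive overall with 92% drinking. The comparison here is also of a package with care management, and section 1.1 reports a median 35% fall in ED visits (p = 0.024) with care management and no naltrexone.

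A reader might also think that section 7.1 assumes an effect in drinkers. The d just under 0.40 is a detectable effect, and the text only says that the authors "posit that it may have a greater effect size in this more severely affected population", after conceding that naltrexone effects have not been robust. Nor does ED observation make this a predictor that the setting could act on: stays of 8 to 23 hours (section 1.1) change a 7-day count by about one day at most.

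**Conclusion.** The point holds as a gap in the Aim 3 specification. Pre-injection abstinence is named in the background as a possible predictor and is not named in the analysis. Separately, the model states no treatment interaction, so it does not test effect modification by abstinence or by anything else on its list. The second gap is the main reason that modification goes untested; omission of the one variable is not the whole cause.

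The size is modest. The primary aim is descriptive, and the sample-size figures are not in dispute. What is lost is an exploratory estimate bearing on the purpose of Aim 3, and that estimate will be wide: about 1.16 SD detectable at N=300 for a yes/no split at an assumed 8.5%, before dropout. Any interaction found would be with XR-NTX+CM as a package, since the design does not separate the drug from care management.

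The conflict between the unqualified efficacy statements in 1.1 and 1.4 and the label summary in 1.4 is a matter of wording. Whether the two cited sources truly disagree cannot be settled from the documents.

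**What to change.** 1. In Aim 3 (section 7.2.2), define days abstinent in the 7 days before randomisation, from the baseline TLFB, in both arms. Enter it in the drinking-outcome model as a baseline covariate and as a treatment-by-abstinent-days interaction. Report the interaction estimate with its confidence interval, labelled exploratory.
2. Reconcile the unqualified efficacy statements in sections 1.1 and 1.4 with the label summary in 1.4.

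The cost is a paragraph of analysis-plan text and one derived variable from data already collected, with no new visit or instrument. The drawback is one more exploratory term, which will be imprecise if few subjects have abstinent days. No change to section 7.1 is needed.

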## 1.5 Dose Rationale

XR-NTX 380mg intramuscular injection every 4 weeks is the FDA approved and recommended dosage for the treatment of alcohol dependence. We will administer XR-NTX according to these guidelines. As per the above data, the extended release preparation is favorable to the oral formulation because it helps address non-adherence. The dosage of XR-NTX 380mg has demonstrated the best efficacy while maintaining safety. The treatment duration is variable in research and clinical practice; the minimum duration is typically 3 months. Duration is generally extended in patients with more severe or refractory alcohol dependence, such as the patients we will be studying. We will plan for each subject to receive 6 months of medication and will explore continuing treatment for up to 12 months of XR-NTX.

## 1.6 Research Risks & Benefits

### 1.6.1 Risk of Study Drug

The study medication (XR-NTX, Vivitrol) was FDA approved in 2006 and will be used for the approved indication(s), so it is not an investigational drug, per se. The FDA has reviewed the protocol and determined that it meets all of the requirements for exemption from the Investigational New Drug (IND) regulations and, therefore, an IND is not required to conduct the investigation. This exemption was requested by the PI because the administration of XR-NTX may deviate slightly from its labeled-use.

XR-NTX is typically recommended for people who are able to abstain from alcohol in an outpatient setting prior to initiation of treatment. The duration of abstinence is not specified. Patients who receive XR-NTX

CONFIDENTIAL

This material is the property of the NYU School of Medicine and Langone Medical Center. Do not disclose or use except as authorized in writing by the study sponsor

in the study may be intoxicated from alcohol when they arrive in the emergency department, but will not be enrolled until medically stable and clinically sober. Patients (potential subjects) may be placed into ED observation for the extended duration of care necessary to achieve this state. If this represents a minor deviation from the VIVITROL labeling, it may affect efficacy but should not represent an additional safety concern. XR-NTX is not aversive therapy and does not cause a disulfiram-like reaction as a result of ethanol ingestion. XR-NTX has been shown to be safe and effective among both individuals who are abstinent and actively drinking. A subject's ability to abstain from drinking prior to an initial XR-NTX injection may predict treatment response. However, this association has not been seen in all studies, including an XR-NTX pilot conducted in Bellevue Hospital primary care. Further, the administration of XR-NTX for the treatment of alcohol dependence users in this study is consistent with current clinical care for alcohol dependent patients in other clinical settings, including Bellevue Hospital Ambulatory care. The administration of XR-NTX in our protocol is based on protocols of ongoing studies of XR-NTX for alcohol dependence in other clinical and community settings, including [name] XR-NTX study in Bellevue Hospital ambulatory care (R01AA020836; S12-02263) and [name]' study in a Seattle community housing program (R01 AA022309), which the FDA also determined was exempt from IND reporting. Also of note, the investigation is not intended to be reported to FDA as a well-controlled study in support of a new indication and there is no intent to use it to support any other significant change in the labeling or advertising of the drug. The investigation does not involve a route of administration, dose, patient population, or other factor that significantly increases the risk associated with the use of the drug product.

**XR-NTX:** This study provides enhanced care management and XR-NTX for treatment of alcohol dependence. According to the FDA prescribing information in all controlled and uncontrolled trials during the premarketing development of XR-NTX, more than 1100 patients with alcohol and/or opioid dependence have been treated with XR-NTX. Approximately 700 patients have been treated for 6 months or more, and more than 400 for 1 year or longer. In controlled trials of 6 months or less in alcohol-dependent patients, 9% of alcohol-dependent patients treated with XR-NTX discontinued treatment due to an adverse event, as compared to 7% of the alcohol-dependent patients treated with placebo. Adverse events in the XR-NTX 380 mg group that led to more dropouts than in the placebo-treated group were injection site reactions (3%), nausea (2%), pregnancy (1%), headache (1%), and suicide-related events (0.3%). In the placebo group, 1% of patients withdrew due to injection site reactions, and 0% of patients withdrew due to the other adverse events. Theoretically naltrexone can cause transient liver inflammation and its packaging has a boxed warning regarding the possibility of serious injury to those with active liver disease and liver function. However, recent clinical trials have demonstrated that does not appear to be hepatotoxic at recommended doses, including in individuals with mild-moderate liver impairment. Liver function will be monitored throughout the trial. We will accommodate (in the ED or clinic) unexpected visits related to side effects and adverse events, and the PI will be available by phone for emergency consultation at any time.

It is thought that mis-injection of XR-NTX into subcutaneous adipose tissue may cause injection site reactions. The PI has been carefully trained on the proper techniques of medication administration, including in his role as medical clinician for the National Institute on Drug Abuse Clinical Trials Network #0048 CURB study (August 2011). Any provider administering XR-NTX to study subjects will receive training as well. The PI will providing training personally and has access to supplemental webinar training resources as part of his membership in the National Institute on Drug Abuse Clinical Trials Network. Providers administering XR-NTX may include physicians, physician assistants, and registered nurses.

XR-NTX also introduces a prolonged mu opioid antagonist blockade, complicating the treatment of acute or chronic pain with opioid medications. Persons receiving XR-NTX will be provided a wallet card identifying them as an XR-NTX patient and containing the PI's name and study phone number. XR-NTX blockade can be 'overridden' due to competitive mu receptor pharmacodynamics with increasing doses of full mu agonists, which should be provided only in a monitored medical setting such as an ED. Persons with chronic pain conditions requiring opioid medications are excluded from enrollment.

Otherwise this is a study of treatment for alcohol dependence, and there is no guarantee subjects will benefit from the intervention, and thus remain chronic, heavy drinkers, with all of the short- and long-term

CONFIDENTIAL

This material is the property of the NYU School of Medicine and Langone Medical Center. Do not disclose or use except as authorized in writing by the study sponsor

risks and hazards alcohol dependence entails. The XR-NTX study represents an evidence-based, FDA approved intervention designed to treat alcohol dependence and minimize these risks, and the PI expects most subjects to derive some minimal benefit from treatment. At the index visit and any point in the trial, subjects who appear to be unable to stop drinking due to severe withdrawal symptoms or who are experiencing severely detrimental consequences of heavy drinking (i.e., job loss, homelessness) will be encouraged to seek admission to inpatient detoxification and specialty treatment through Bellevue Hospital. Withdrawal will be treated in the ED during the index visit as needed per standard of care. As per usual care, detoxification and intensive outpatient alcohol specialty services are immediately available to all subjects through the Bellevue Hospital Chemical Dependency programs, including same-day admissions to our detoxification unit, regardless of insurance status or ability to pay. Most of the risks described are well defined side effects naltrexone and XR-NTX or of on-going alcohol dependence. The additional risks of naltrexone treatment are small.

Protection against Risk (XR-NTX): As per exclusion criteria, the PI will avoid administering XR-NTX in patients with medical conditions that would contraindicate its use. Specifically, XR-NTX will not be used in: active opioid dependence (including any individual whose urine drug screen is positive for opioids), acute or chronic pain requiring opioid treatment, acute liver injury/failure (liver aminotransferase concentrations  $>5$  times the upper limit of normal), any medical condition considered by the PI to be incompatible with or unsafe for study inclusion (e.g. expectation of future opioid needs), lack of decisional capacity, refusal to consent, currently being prescribed outpatient addiction pharmacotherapy (other than treatment of alcohol withdrawal), previous significant adverse reaction to naltrexone, poly(lactide-co-glycolide, carboxymethylcellulose, or any other components of the diluent, body habitus that precludes safe injection, children, or pregnancy. The PI will assess liver function prior to enrollment; persons with liver aminotransferase concentrations  $>5$  times the upper limit of normal will not be eligible for enrollment. Subjects will be monitored for signs and symptoms of liver injury at subsequent XR-NTX administration visits and research visits. Subjects in both arms will have their liver enzymes tested at enrollment and at the 3-, 6-, and 12-month research visits. The PI will repeat liver enzyme testing if subject receiving XR-NTX through the study has signs or symptoms of liver injury. If the liver aminotransferase concentrations rise to  $>5$  times the upper limit of normal, the laboratory tests will be repeated in one week. If liver enzymes are persistently elevated or if the individual is symptomatic, study medication will be discontinued and the subject will be referred for a Hepatology evaluation.

In case of an emergency situation requiring opioids, subjects will be provided with a card showing that they have (or have not) received XR-NTX. This card will provide detailed information to medical personnel describing the special precautions necessary in the event that the subject should require pain management. Specifically, the amount of opioids necessary for analgesia may be greater than usual, and the resulting respiratory depression may be deeper and more prolonged. As a result, a rapidly acting analgesic that minimizes respiratory depression is preferred and the amount of the analgesic administration titrated to the needs of the patient in a setting equipped and staffed for cardiopulmonary resuscitation. The name of and contact information for the study PI and phone number of will be listed on the card in the event of an emergency. Unexpected visits related to side effects and adverse events will be accommodated (in the ED or clinic), and the PI will be available by phone for emergency consultation at any time.

